## 5.5. Outline of study procedures

**Table 6 List of study procedures**

Type of contact	Epoch 001					Epoch 002		
	Visit 1	Visit 2	Visit 3	Visit 4 (TC1)	Visit 5 (TC2)	Visit 6	Visit 7	Visit 8 (TC3)
Time point (s)	Day 0	Day 21	Day 42	Day 90	Day 240	Day 385	Day 392	Day 415
Sampling timepoint(s)	Pre-Vacc 1	Pre-Vacc 2	Post-Vacc 2			Post-Vacc 2	Post-Vacc 3	
Informed consent	●							
Check inclusion / exclusion criteria	●							
Check contraindications to vaccination *	●	●				●		
Medical history	●							
Seasonal influenza vaccination history 	●							
Collect demographic data	●							
Physical examination	●							
Measure/record height and weight	●							
Brief (symptom directed) physical examination		○	○			○	○	
Record concomitant medications and vaccinations	●	●	●	●	●	●	●	●
Pre-vaccination body temperature /vital signs	●	●				●		
Study group and treatment number allocation	●							
Treatment number allocation for subsequent doses		●				●		
Blood sampling for assessment of humoral immune response (approx. 2.5 mL venous blood)	●		●			●	●	
Blood sampling for assessment of CMI response (approx. 2.0 mL venous blood)	●		●			●	●	
Vaccine dose preparation by unblinded staff	○	○				○		
Vaccine administration (record treatment number)	●	●				●		
Provide training / Distribute diary cards 	○	○				○	○	
Parent/LAR records solicited AEs  (beginning on the day of the dose and for the following six days; e.g., Day 0 – 6)	○	○				○		
Parent/LAR records unsolicited AEs beginning with day of vaccination and continuing for next 20 (doses 1 and 2) or 29 (booster dose) days	○	○				○	○	○
Parent/LAR returns diary cards		○	○				○	

Type of contact	Epoch 001				Epoch 002			
	Visit 1	Visit 2	Visit 3	Visit 4 (TC1)	Visit 5 (TC2)	Visit 6	Visit 7	Visit 8 (TC3)
Time point (s)	Day 0	Day 21	Day 42	Day 90	Day 240	Day 385	Day 392	Day 415
Sampling timepoint(s)	Pre-Vacc 1	Pre-Vacc 2	Post-Vacc 2			Post-Vacc 2	Post-Vacc 3	
Investigator transcribes diary card data		●	●				●	●
Report all non-serious adverse events 	●	●	●			●	●	●
Report non-serious adverse events leading to study withdrawal	●	●	●	●	●	●	●	●
Report current/intercurrent medical conditions	●	●	●			●	●	●
Report medically attended events 	●	●	●	●	●	●	●	●
Report serious adverse events 	●	●	●	●	●	●	●	●
Report pIMDs 	●	●	●	●	●	●	●	●
Report SAEs related to study participation or GSK concomitant product or any fatal SAE	●	●	●	●	●	●	●	●
Study conclusion								●

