Note: The double-line border following Day 42 indicates analyses will be performed on all data obtained up to this time point; Pre-Vacc: Pre-vaccination. Post-Vacc: Post-vaccination.. TC = telephone contact. ● is used to indicate a study procedure that requires documentation in the individual eCRF.

○ is used to indicate a study procedure that does not require documentation in the individual eCRF

\* If any, it has to be recorded in medical history (prior first vaccination) or in AE/SAE.

1. Influenza vaccination history will include all previous seasonal influenza vaccination(s)]
2. Diary cards used to capture both solicited (for 7 days following each dose) and unsolicited events (for 21 days after doses 1 and 2; for 30 days after booster dose) are provided at the time of each vaccination and collected at the next visit after each vaccination.
3. Recording of intensity and duration of solicited local symptoms and of occurrence, intensity, duration, and relationship of each solicited general AE and unsolicited AE;
4. Recording of intensity, duration and relationship to vaccination of each event reported. Reported events will be searched for AESIs.

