### **8.2.1. Time periods for detecting and recording adverse events/SAEs**

All solicited and unsolicited AEs must be recorded into the appropriate section of the eCRF, irrespective of intensity or whether or not they are considered vaccination-related.

Solicited AEs must be recorded for 7 days, i.e. on the day of each study vaccination and for the next 6 days after (i.e., Day 0 to Day 6 (dose 1); Day 21 to Day 27 (dose 2); Day 385 to Day 392 (booster dose)).

The time period for collecting and recording information about occurrences of AEs leading to withdrawal from the study, MAEs, pIMDs and SAEs will begin with the first study vaccine dose and will end when the subject is discharged from the study. See Section [8.3](#) for special instructions on reporting of pIMDs and SAEs.

In addition to the above-mentioned reporting requirements and in order to fulfil international reporting obligations, SAEs that are related to study participation (i.e. protocol-mandated procedures, invasive tests, a change from existing therapy) or are related to a concurrent GSK medication/vaccine will be collected and recorded from the time the subject consents to participate in the study until she/he is discharged from the study.

Occurrences of all other unsolicited AEs must be recorded from the time of the first receipt of study vaccine through completion of the Day 42 visit (Day 0 to Day 42) as well as on day of booster dose (Day 385 and 30 days after booster to Day 415) or until the subject is withdrawn or lost to follow-up.

The clinical database will be searched for events corresponding to AESIs; this will include any AEs reported from Day 0 to Day 42 or within 30 days post-booster, as well as any MAEs, SAEs or pIMDs reported during the entire study period.

[Table 17](#) provides an overview of the protocol-required reporting periods for collecting safety information.

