  - Occurrence of each solicited general AEs during a 7-day follow-up period (i.e., day of vaccination and 6 subsequent days) after any vaccination.
    - Percentage, intensity, duration and relationship to vaccination of solicited general AEs during a 7-day follow-up period (Day 0-Day 6) after any vaccination.
- Unsolicited adverse events (AEs)
  - For the primary series: occurrence and relationship to vaccination of unsolicited AEs within 21 days after each vaccine dose.
    - Percentage, intensity and relationship to vaccination of unsolicited AEs during a 21-day follow-up period (Day 0-Day 20) after each vaccine dose.
  - For the booster dose [unadjuvanted]: occurrence and relationship to vaccination of unsolicited AEs within 30 days after vaccination
    - Percentage, intensity and relationship to vaccination of unsolicited AEs during a 30-day follow-up period.
  - Occurrence and relationship to vaccination of adverse events with MAEs during the entire study period.
    - Percentage and relationship to vaccination of MAEs during the entire study period.
  - Occurrence and relationship to vaccination of pIMDs, SAEs, AESIs during the entire study period.
    - Percentage and relationship to vaccination of pIMDs, SAEs, AESIs during the entire study period.

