6.1.3. Analysis for safety

- Safety data will be analyzed based on the TVC.
- Analysis will be of subject incidence rates of solicited and unsolicited adverse events (AEs), by solicited local and general AEs terms, and, for unsolicited AEs, by MedDRA preferred term and system organ class. Safety data will be summarized for all subjects by treatment group. The incidence of solicited local and general AEs occurring during 7 days after vaccination will be tabulated with exact 95% CI for each treatment group. The same calculations will be performed for AEs of any

intensity, those with intensity Grade ≥ 2 , and those with intensity of Grade 3, as well as for solicited general events assessed as related to vaccination. All solicited local AEs are considered to be related to vaccination.

- The percentage of subjects with at least one report of an unsolicited AE classified by MedDRA (System Organ Class and Preferred Term) 21 days after each primary vaccination will be tabulated with exact 95% CI for each treatment group. The same tabulation will be performed for Grade 3 unsolicited AEs and for unsolicited AEs that are considered by the investigator to be possibly or probably related to vaccination.
- The percentage of subjects with at least one report of an unsolicited AE classified by MedDRA (System Organ Class and Preferred Term) 30 days after the booster vaccination will be tabulated with exact 95% CI. The same tabulation will be performed for Grade 3 unsolicited AEs and for unsolicited AEs that are considered by the investigator to be possibly or probably related to vaccination.
- The proportion of subjects who begin at least one new concomitant medication during the first 42 days after primary vaccination will be calculated with 95% CI.
- MAEs, AESIs, SAEs, and pIMDs will be summarized through the entire study period. In addition, serious AEs and withdrawals due to AE(s) will be described in detail.

The pIMD listings will include pIMDs reported by the Investigator and those identified from the clinical database search using a list of pre-specified pIMD PTs.

The AESIs listings will include AESIs identified from the clinical database search using a list of pre-specified AESIs PTs and SMQs. The AESIs will include the events listed below and the MedDRA PT or SMQ used to identify reports of these events is provided in parentheses:

- Anaphylaxis (narrow SMQs “Anaphylactic reaction” and “Angioedema”)
- Bell’s palsy (MedDRA PT “VIIth nerve palsy”)

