7.1.3. Reactogenicity and safety

Incidence rates of AEs will be calculated as the number of subjects who experience the event, divided by the number of subjects in the safety analysis cohort (the TVC).

Handling of missing safety data:

- **Solicited AEs:** For a given subject and the analysis of solicited AEs within 7 days post-vaccination (Days 0 through 6), missing or non-evaluable measurements will not be replaced.
 - The analysis of the solicited AEs will include only vaccinated subjects and doses with documented safety data (i.e., symptom screen/sheet completed, including the response ‘Yes’ or ‘No’ to the solicited symptom page).
 - Subjects who answered “Yes” in the solicited symptom page, but had all symptoms missing are considered as having no solicited symptoms.
 - Subjects who answered ‘Yes’ to the presence of a specific symptom but partially recorded the daily measurement (e.g. intensity missing for Day 3) over the considered solicited period will be included in the summaries and classified according to their maximum observed daily recording over the solicited period.
 - Subjects who answered ‘Yes’ to the presence of a specific symptom but recorded no daily measurement over the considered solicited period will not be counted in the summary of symptoms by grade/category but will be part of the summary corresponding to the ‘All’ category for that symptom.
- **Unsolicited AEs:** For the analysis of unsolicited AEs/MAEs/SAEs/pIMDs/AESIs, all vaccinated subjects will be considered and subjects who did not report an event will be considered as subjects without an event.
- **Concomitant medication and vaccination:** For the analysis of concomitant medications and vaccinations, all vaccinated subjects will be considered and subjects who did not report an event will be considered as subjects without an event.

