7.1.3.1. Counting rule

Event	N used for deriving % per subject for vaccination phase
Solicited general symptom	All subjects with at least one solicited general symptom documented as either present or absent (i.e. symptom screen completed)
Solicited local symptom	All subjects with at least one solicited local symptom documented as either present or absent (i.e. symptom screen completed)
Unsolicited symptom MAEs/SAEs/pIMDs/AESIs	All subjects with study vaccine administered
Concomitant medication	All subjects with study vaccine administered
Concomitant vaccination	All subjects with study vaccine administered

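### Recording of routine unsolicited AEs ends at the Day 42 visit, which may come as early as 13 days after dose 2, so the 21-day dose 2 incidence can be understated (minor)

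*Protocol*

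**What the plan says.** **What is reported.** Protocol 10.2 defines the primary-series endpoint as "Percentage, intensity and relationship to vaccination of unsolicited AEs during a 21-day follow-up period (Day 0-Day 20) after each vaccine dose". SAP 6.1.3 follows it: the percentage of subjects with at least one unsolicited AE "21 days after each primary vaccination will be tabulated with exact 95% CI for each treatment group".

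**What is collected.** Table 6 has parents record unsolicited AEs from the day of vaccination, "continuing for next 20 (doses 1 and 2) or 29 (booster dose) days". Footnote 2 adds that the diary cards "are provided at the time of each vaccination and collected at the next visit after each vaccination", which for dose 2 is Visit 3. Protocol 8.2.1 ends the primary-series period for this class of events at the same visit: occurrences "must be recorded from the time of the first receipt of study vaccine through completion of the Day 42 visit". Medically attended events (MAEs), potential immune-mediated diseases (pIMDs), serious AEs (SAEs) and AEs leading to withdrawal are collected until discharge.

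**When the visits fall.** Table 7 allows Visit 2 at 18 to 25 days and Visit 3 at 38 to 46 days, both counted from Visit 1. It has no row for Visit 2 to Visit 3.

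**How silence is counted.** For unsolicited AEs, SAP 7.1.3 states that "all vaccinated subjects will be considered and subjects who did not report an event will be considered as subjects without an event". The denominator in SAP 7.1.3.1 is "All subjects with study vaccine administered". Neither section has a rule for a child whose 21 days were not fully recorded.

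**The concern.** The endpoint runs for a fixed number of days from dose 2, whereas collection stops at a visit timed from dose 1. When dose 2 is late or Visit 3 is early, the end of the dose 2 window is not recorded, yet the child is tabulated as fully observed.

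No later step recovers the missing days. Table 17 is blank for this class of events at Days 90 and 240. Table 6 shows no general non-serious AE reporting at those two contacts and no new diary card at Visit 3. Protocol 10.8.1.3 and SAP 8.1.3 treat reporting up to the Day 42 visit as equivalent to 21 days after each dose, which Table 7 does not guarantee.

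The booster is protected: its closing contact is timed from the booster visit with a minimum of 30 days, and a diary card is also handed out at Visit 7.

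At stake is the absolute dose 2 incidence for a stated secondary safety endpoint. Any error from this source is downward.

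**Working it through.** **Inputs.** Dose 2 on Day a, a = 18 to 25; Visit 3 on Day b, b = 38 to 46 (Table 7). Endpoint window: Days 0 to 20 after dose 2, 21 days (Protocol 10.2). Recording includes the day of Visit 3, because 8.2.1 runs through completion of that visit.

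**Formulas.** Gap g = b − a. Days covered = min(21, g + 1). Days lost = max(0, 20 − g). Coverage is complete when g is at least 20.

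**The plan's own figure.** Nominal schedule: g = 42 − 21 = 21, so 21 days are covered and none lost. The stated 21-day window is reproduced.

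**Extremes within the allowed windows**
- Shortest: g = 38 − 25 = 13; Days 0 to 13, or 14 days, covered; 20 − 13 = 7 lost; 7/21 = 33%.
- Longest: g = 46 − 18 = 28; none lost.
- Latest dose 2 with Visit 3 on target: g = 42 − 25 = 17; 18 days covered, 3 lost.

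**Scenario 1 (assumed): uniform, independent visit days.** There are 8 × 9 = 72 day pairs.

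| Gap (days) | Pairs | Days lost each | Total lost |
|---|---|---|---|
| 13 | 1 | 7 | 7 |
| 14 | 2 | 6 | 12 |
| 15 | 3 | 5 | 15 |
| 16 | 4 | 4 | 16 |
| 17 | 5 | 3 | 15 |
| 18 | 6 | 2 | 12 |
| 19 | 7 | 1 | 7 |
| 20 to 28 | 44 | 0 | 0 |

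Short pairs: 28/72 = 39%. Mean loss: 84/72 = 1.17 days, and 1.17/21 = 5.6% of the window.

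**Scenario 2 (assumed): visits clustered around Days 21 and 42**, with normal weights truncated to the allowed windows.

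| SD (days) | Share with g under 20 | Mean loss (days) | Share of window |
|---|---|---|---|
| 1.5 | 24% | 0.42 | 2.0% |
| 2 | 30% | 0.64 | 3.0% |
| 3 | 35% | 0.89 | 4.2% |

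The 13-day case is 1 of 72 pairs in scenario 1 and at most 0.4% of children in scenario 2.

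**Effect on an incidence (constant hazard assumed).** A child with d days covered is observed to have an event with probability 1 − (1 − p)^(d/21). For a true 21-day incidence of p = 20%:
- every child seen at 13 days, the extreme: 1 − 0.8^(14/21) = 13.8%;
- a quarter of children seen at 13 days, the rest complete: 0.25 × 13.8 + 0.75 × 20 = 18.5%;
- uniform visits, averaged over the 72 pairs: 19.0%;
- nominal schedule: 20%.

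These percentages apply only to events outside the classes collected to discharge.

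**The case against.** The strongest reply is that little is lost. The optimal schedule covers the whole window, and Table 7 tells sites to use the optimal interval whenever possible, which argues against the uniform scenario. Events that are medically attended, serious, immune-mediated or a cause of withdrawal are still collected at later contacts, and onset day can place them in the window. Only minor events with onset in the last few days can be missed. Day 42 is also when routine vaccines become permitted (Protocol 4.3 and 6.7.2), so it is a sensible stopping point. All of this stands, and it is why the point is minor. It does not remove the mismatch or supply the missing SAP rule. The 7-day maximum also holds only within the allowed windows: leaving them affects eligibility for the according-to-protocol immunogenicity cohort, while safety uses the total vaccinated cohort.

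A reader might infer more than the documents support:

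- **That dose 2 is biased downward relative to dose 1.** SAP 7.1.3.3 assigns onset to the most recent vaccination. If Visit 2 falls on Days 18 to 20, the end of the dose 1 window is counted under dose 2. Under the clustered weights (SD 1.5, 2, 3), dose 1 loses on average 0.54, 0.64 and 0.71 days against 0.42, 0.64 and 0.89 for dose 2, and the displaced events add to dose 2. The net direction is not established, and the safety analysis sections specify no such comparison for unsolicited AEs.
- **That the fever question is affected.** Solicited fever is recorded for 7 days and enters the primary index for 3 days after each dose. Both periods end before the shortest allowed gap of 13 days.
- **That the ranking of regimens is distorted.** Arms are randomised and observer-blind with identical visit windows. Nothing in the documents suggests that truncation would differ by arm.
- **That all non-serious unsolicited AEs stop at Day 42.** Non-serious MAEs, pIMDs and AEs leading to withdrawal do not.

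**Conclusion.** The point holds as a minor inconsistency between collection and endpoint. A site that follows the plan exactly can stop recording this class of AE 13 days after dose 2, and the SAP then counts the child as observed and event-free for 21 days. The dose 2 percentage can be understated; whether it is depends on visit timing.

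The loss is zero on the nominal schedule and at most 7 of 21 days (33%) for one child within the allowed windows. The group averages, 1.2 days if visits are uniform and 0.4 to 0.9 days if clustered, are assumed scenarios, because the documents give neither the distribution of visit days nor the timing of events. No dose 1 versus dose 2 bias and no effect on regimen ranking is claimed.

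**What to change.** **Protocol.** Reconcile 8.2.1 and Tables 6, 7 and 17 with the 21-day endpoint. End the primary-series period for unsolicited AEs at the later of the Day 42 visit and 20 days after dose 2. When Visit 3 comes earlier, let the parent keep the unsolicited AE page and collect the remaining days at an already scheduled contact, such as the Day 90 call.

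**SAP.** In 6.1.3 and 7.1.3, report by group the number of children whose recording ended before Day 20 after dose 2, and repeat the dose 2 unsolicited AE table in children with the full window. If collection is already complete, this change alone suffices.

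**Cost.** Wording and one repeated table, with no extra visit. The last few days would rest on later recall, since Table 7 places the Day 90 contact at Days 80 to 100. Routine vaccines allowed from the Day 42 visit may contribute events, so events with onset after such a vaccine should be flagged.

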**Table 17 Reporting periods for collecting safety information :**

Study activity	All groups											
	Visit 1 V1		-	Visit 2 V2		-	Visit 3 V3	Visit 4 (TC 1)	Visit 5 (TC 2)	Visit 6	Visit 7	Visit 8 (TC 3)
	D0 	D0 –D6	D7-D20	D21	D21-D27	D28 – D41	D42	D90	D240	D385	D392	D415
Solicited AEs (local and general)	DC, SP	DC		DC, SP	DC						DC, SP	
Unsolicited MAEs, SAEs and pIMDs *	DC, SP	DC	DC	DC, SP	DC	DC	DC, SP	I	I	DC, SP	DC, SP	TC, I
Unsolicited SAEs related to study participation or concurrent GSK medication/vaccine *	DC, SP	DC	DC	DC, SP	DC	DC	DC, SP	I	I	DC, SP	DC, SP	TC, I
Unsolicited AEs related to study withdrawal *	DC, SP	DC	DC	DC, SP	DC	DC	DC, SP	I	I	DC, SP	DC, SP	TC, I
All other unsolicited AEs *	DC, SP	DC	DC	DC, SP	DC	DC	DC, SP			DC, SP	DC, SP	TC, I

V: vaccination;; D: Day, AE= adverse event; MAE = medically attended adverse event; SAE = serious adverse event, DC = diary card, TC, I = phone contact scripted interview, SP = interaction with site personnel at study visit. Data will be reported to GSK via electronic Case Report Form.

Solicited AE diary card data collected for 7 days after dose 1 to be reviewed at Day 21 visit. Solicited AE diary card data collected for 7 days after dose 2 to be reviewed at Day 42 visit.

Events that occur prior to vaccination are only to be reported if they are SAEs related to study participation or to a GSK concomitant product.

\* Reported events will be searched for AESIs.

## **8.2.2. Post-Study adverse events/SAEs**

A post-study AE is defined as any event that occurs outside of the AE reporting period defined in [Table 17](#). Investigators are not obligated to actively seek AEs in former study participants. However, if the investigator learns of any *SAE* at any time after a subject has been discharged from the study, and he/she considers the event reasonably related to the investigational vaccine(s)/product(s), the investigator will promptly notify the Study Contact for Reporting *SAEs*.

## **8.2.3. Evaluation of adverse events/SAEs**

### **8.2.3.1. Active questioning to detect adverse events/SAEs**

As a consistent method of collecting AEs, the subject or the subject's parent(s)/LAR(s) should be asked a non-leading question such as:

*'Have you felt different in any way since receiving the vaccine(s)/product(s) or since the previous visit?'*

*'Has your child acted differently or felt different in any way since receiving the vaccine(s)/product(s) or since the last visit?'*

When an AE occurs, it is the responsibility of the investigator to review all documentation (e.g. hospital progress notes, laboratory and diagnostics reports) relative to the event. The investigator will then record all relevant information regarding an AE in the eCRF. The investigator is not allowed to send photocopies of the subject's medical records to GSK Biologicals instead of appropriately completing the eCRF. However, there may be instances when copies of medical records for certain cases are requested by GSK Biologicals. In this instance, all subject identifiers will be blinded on the copies of the medical records prior to submission to GSK Biologicals.

The investigator will attempt to establish a diagnosis pertaining to the event based on signs, symptoms, and/or other clinical information. In such cases, the diagnosis should be documented as the AE and not the individual signs/symptoms.

### 8.2.3.2. Assessment of intensity

#### 8.2.3.2.1. *Solicited AEs*

The intensity of the following solicited AEs will be assessed as described:

**Table 18 Intensity scales for solicited symptoms in infants/toddlers and children less than 6 years of age**

Adverse Event	Intensity grade	Parameter
Pain at injection site	0	None
	1	Mild: Minor reaction to touch
	2	Moderate: Cries/protests on touch
	3	Severe: Cries when limb is moved/spontaneously painful
Redness at injection site		Record greatest surface diameter in mm
Swelling at injection site		Record greatest surface diameter in mm
Fever*		Record temperature in °C/°F
Irritability/Fussiness	0	Behaviour as usual
	1	Mild: Crying more than usual/no effect on normal activity
	2	Moderate: Crying more than usual/interferes with normal activity
	3	Severe: Crying that cannot be comforted/prevents normal activity
Drowsiness	0	Behaviour as usual
	1	Mild: Drowsiness easily tolerated
	2	Moderate: Drowsiness that interferes with normal activity
	3	Severe: Drowsiness that prevents normal activity
Loss of appetite	0	Appetite as usual
	1	Mild: Eating less than usual/no effect on normal activity
	2	Moderate: Eating less than usual/interferes with normal activity
	3	Severe: Not eating at all

\*Fever is defined as temperature  $\geq 38.0^{\circ}\text{C} / 100.4^{\circ}\text{F}$  assessed by any route (axillary preferred)

The maximum intensity of local injection site redness or swelling will be scored at GSK Biologicals as follows:

0	:	$\leq 20$ mm
1	:	$> 20$ to $50$ mm
2	:	$> 50$ to $100$ mm
3	:	$> 100$ mm

Body temperatures will be scored at GSK Biologicals as follows:

0	$< 38.0^{\circ}\text{C} (< 100.4^{\circ}\text{F})$
1	$\geq 38.0 - 38.4^{\circ}\text{C} (\geq 100.4 - 101.2^{\circ}\text{F})$
2	$\geq 38.5 - 38.9^{\circ}\text{C} (\geq 101.3 - 102.1^{\circ}\text{F})$
3	$\geq 39.0 - 40^{\circ}\text{C} (\geq 102.2 - 104.0^{\circ}\text{F})$
4	$>40.0^{\circ}\text{C} (>104.0^{\circ}\text{F})$

